We will test the hypotheses related to examining effectiveness of participation in the RTS in leading to reductions in CSEC perpetration (primary outcome), as well as reductions in CSEC victimization and TDV and SV victimization and perpetration and increases in bystander intervention in CSEC situations (secondary outcomes). To improve the rigor of analyses for Aim 2a, we will use propensity-score analysis to reduce the impact of selection bias, and latent constructs, when possible, to reduce measurement error, reduce paths and variables, and increase statistical power (MacCallum et al., 1996). This approach produces rigorous estimates of causal effects within the context of quasi-experimental designs when random assignment is not possible by controlling confounders, including selection effects¹⁴⁴. This approach will use four analytic steps: (1) estimate propensity scores in a separate analysis, (2) use the propensity scores to adjust for confounding, (3) assess balance, and (4) estimate the propensity score-adjusted treatment effects (Lanza et al., 2013). In step 1, to estimate the propensity score, we will consider all pertinent confounders and covariates (see Measurement Table 3). This step will use logistic regression of condition on the potential confounders to obtain each student's propensity score. All measured confounders that are predictive of selection into the experimental conditions and the outcomes will be included in the propensity model. Standardized mean differences in covariate values across treatment and comparison conditions will be used to determine the final set of confounders to include in estimating the propensity score. In step 2, an initial treatment effect model is estimated that adjusts for confounding using the propensity score. We will use inverse probability weighting (IPTW) to adjust for confounding. The standardized mean differences between experimental groups are computed on the weighted sample included the IPTW-adjusted propensity score (Step 2). If IPTW does not provide optimal balance, then other methods will be considered (e.g., matching). Then Step 3 is used to determine balance on the potential confounders included in the propensity score across the experimental groups. The goal is to determine whether there are any differences remaining on the confounders between experimental groups (balance = standardized mean differences $< |0.2|$ after adjustment). Confounders will be adjusted and the propensity score model (Step 1) will be re-estimated until balance is reached. Once balance is determined, the outcome analysis will be conducted in Step 4 via SEM. The experimental effect of interest will be the Average Treatment Effect (ATE), which is the population-level average effect of condition on the primary and secondary outcomes as detailed in the logic model. The effects of interest quantified are differences between experimental conditions at post-test and follow-up on outcomes (for continuous measures), the propensity score as a covariate. These effects indicate whether the outcomes in the experimental condition differ significantly from those in the comparison condition. At post-test and follow-up, we expect the difference between the experimental conditions to be significantly greater than zero, reflecting better outcomes for those in the RTS program as compared to those in the wait-list condition, after adjusting for the

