
propensity score. For categorical variables, logistic regression will be used to examine differences in prevalence by condition. The experimental condition is the independent variable in these models. Multilevel modeling is not possible given the small number of schools; thus, school will be included as a covariate. Classroom will be used as a cluster variable to adjust the standard errors for nesting. Models for Step 4 will be evaluated for overall model fit via χ^2 statistic, RMSEA :s .08, SRMR :s .10, and CFI \geq .90. We will evaluate our hypotheses across several indicators, including significance (p), confidence intervals, and the standardized difference between groups (d), as well as the directionality of included path coefficients, and odds ratios.

Mediation and Moderation Analyses (Aim 2b).

We will assess mediators (e.g., perceptions of norms intolerant of CSEC) and demographic moderators (e.g., gender) of program effectiveness, including the propensity score and school as covariates in all models. To test for mediation, we used the product of coefficients method using bias-corrected bootstrapping with 1000 resamples to calculate the confidence intervals¹⁴⁵ (MacKinnon, 2012). For our moderators (e.g., age, gender, racial groups, sexual orientation), we will estimate structural equation multiple group models, first allowing estimation of the path coefficients to vary freely across groups, and then constraining paths to be equal when a structural path coefficient of interest was significant for one group and not the other group. We will conduct model comparisons using the chi-square (χ^2) difference test (i.e., χ^2 , $p < .05$ indicating moderation).

Aim 2c. Descriptive statistics will be used to examine the extent to which sessions were delivered with fidelity. Process observations will be analyzed using thematic analysis as described above for Aim 1b.

Aim 2d. Descriptive statistics will be used to examine the frequency of responses to close-ended questions (e.g., To what extend did you like the session today?). Open-ended questions will be analyzed using thematic analysis as described above for Aim 1b.

Aim 2e. Interview data will be analyzed using thematic analysis as described above for Aim 1b.

Aim 2f. The purpose of this aim is to determine costs associated with the program implementation to inform future economic evaluation of the RTS. The process for documenting costs are described in Section C.18.

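### Balance is checked only in the whole sample, yet the same propensity score adjusts the multiple-group moderation models, so confounding that differs by group can pass the check and can appear as moderation

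*SAP*

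**What the plan says.** The SAP describes Aim 2a as an analysis "within the context of quasi-experimental designs when random assignment is not possible by controlling confounders, including selection effects", so the propensity score carries the causal claim. Under Proposed Analyses, Outcome Analyses (Aim 2a):

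- Step 1: "This step will use logistic regression of condition on the potential confounders to obtain each student's propensity score". One model gives one score per student. No confounder-by-moderator terms and no group-specific models are stated.
- Step 2: "The standardized mean differences between experimental groups are computed on the weighted sample", after inverse probability weighting.
- Step 3: "Then Step 3 is used to determine balance on the potential confounders included in the propensity score across the experimental groups". The pass mark is "balance = standardized mean differences $< |0.2|$ after adjustment", and "the propensity score model (Step 1) will be re-estimated until balance is reached".
- Step 4: the effect of interest is the population-level average treatment effect.

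Under Mediation and Moderation Analyses (Aim 2b), the adjustment is described as "including the propensity score and school as covariates in all models". For age, gender, racial group and sexual orientation, "we will estimate structural equation multiple group models". Paths are first free across groups. A path is then constrained to equality when it is significant in one group and not in the other, and a chi-square difference with p < .05 is read as moderation. Balance within a moderator group is not mentioned. Whether the weights carry over to Aim 2b is not stated either; only the score as covariate is named.

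The power section for Aim 2b plans for a moderation difference of b=.20 and expects groups as small as 10% (n=724) and 2.5% (n=181).

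**The concern.** Balance over the whole sample does not imply balance inside each moderator group. Suppose girls with a high value of some risk factor tend to end up in RTS, and boys with a high value tend to end up in the wait-list condition. The two imbalances cancel in the whole sample, Step 3 passes, and nothing prompts a new propensity model. The Aim 2b test compares the group-specific effects, which is where the leftover confounding sits.

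At stake is the answer to the question of for whom RTS works. The protocol names wide dissemination as a goal if the programme proves effective, and a false subgroup finding by gender, race or sexual orientation could misdirect it.

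**Working it through.** The SAP gives no figure on this point to reproduce. The check has two parts: what the Step 3 rule can detect, and how large the effect of a miss could be.

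**Inputs from the SAP:** N=7,241; balance limit |0.2|; groups of 10% and 2.5%; moderation test at .05; planned moderation difference b=.20; CSEC perpetration incidence 1% to 5%.

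**Assumed, not in the documents:** the confounder-outcome path (.1, .3 or .4 per SD), the strength of selection in each group, conditions 1:1, a 50/50 moderator unless stated, unit residual SD, no clustering and no school covariate.

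**1. What the whole-sample check can see.** With similar condition ratios across groups, whole-sample SMD ≈ sum of (group share × within-group SMD).

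- 50/50 moderator, +.20 and -.20: .5 × .20 + .5 × (-.20) = 0. Passes.
- 10% group with SMD 1.0, balance elsewhere: .10 × 1.0 = .10. Passes.
- 2.5% group with SMD 1.0, balance elsewhere: .025 × 1.0 = .025. Passes.

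For the small groups, opposite signs are not needed. The within-group SMD would have to reach .2/.10 = 2.0 or .2/.025 = 8.0 before the check failed.

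**2. Spurious effect difference.** Difference ≈ path × (SMD in group A − SMD in group B).

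- Path .3, ±.10: .3 × .20 = .06.
- Path .3, ±.20: .3 × .40 = .12. Path .4, ±.15: .4 × .30 = .12. This is .12/.20 = 60% of the planned b.
- Path .1, ±.10: .1 × .20 = .02.

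**3. How often it would be declared.** With 7,241/2 ≈ 3,620 per group, the SE of one group's effect is 2/√3,620 = .0332, and the SE of the difference is .0332 × √2 = .0470. Hence z = .06/.0470 = 1.28 (rejection about 25%), .12/.0470 = 2.55 (about 72%) and .02/.0470 = .43 (about 7%).

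Simulation of the written steps (main-effects logistic score, weighting, SMD check, group regressions with the score as covariate, test of equal effects) agrees. Ranges are across repeated runs with slightly different data-generating details. The screen is the SAP's rule that a path is constrained only if significant in one group and not the other.

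| Setting, no true effect | Whole-sample SMD | Spurious difference | False moderation, no screen | With screen |
|---|---|---|---|---|
| ±.10, path .3 | .00 | .06 | 19%-24% | 12%-15% |
| ±.20, path .3, or ±.15, path .4 | .00 | .12 | 60%-75% | 35%-45% |
| ±.10, path .1 | .00 | .02 | 5%-7% | 4% |
| 10% group at .27, others -.03, path .3 | .00 | .08 | 19% | 16% |
| 2.5% group at .48, others -.01, path .3 | .00 | .14 | 18% | 16% |
| Same-direction selection in both groups | .00 | .00 | 4.5% | 3.5% |

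Using the score as covariate without weights changes little (23% and 72% in the first two rows). Letting the score's path differ by group does not help, because when the slopes cancel the score carries almost no information on that confounder.

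**4. Clustering.** The SAP adjusts standard errors for classroom. With an assumed design effect of 1.5 to 2, a difference of .12 gives 44%-55% without the screen and 29%-36% with it; .06 gives 15%-18% and 10%-12%. Clustering dilutes the rate but leaves the bias.

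**5. Rare binary outcomes.** On the log-odds scale, the SE of the difference is √(8/(3,620 × p(1−p))): .47 at p=1% and .22 at p=5%. A log-odds bias of .06 to .12 gives rejection of about 5%-6% at 1% and 6%-9% at 5%. Simulation gave 5%-7% and 7%-8%, or 2%-4% and about 5% with the screen.

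**6. After the change.** With moderator-by-confounder terms in the propensity model, within-group SMDs fall to about .00, the spurious difference to near zero, and false moderation to about 3%-6.5%.

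**The case against.** The strongest reply is that the harm is conditional. It needs selection on a confounder to differ by moderator group, and that confounder to predict the outcome. Nothing in the documents says that selection runs in opposite directions for any groups; how students come to be in RTS or wait-list is not described in them. Slopes that cancel exactly are a constructed case. This stands: the claim is that imbalance can appear as moderation, not that it will.

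A reader might also take 60%-75% as the error rate of the plan. The documents do not support that. The figure omits the SAP's screen, rests on assumed slopes and applies to continuous outcomes. Nor does the screen's effect run one way: with ±.30 and path .3 it lowers 97% to 33%, because both groups become significant in opposite directions, whereas with ±.20 and a uniform true effect of d=.06 the rate stays at 69%.

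A further tempting reading is that the primary result is compromised. It is not. Where the confounder acts alike in both groups the biases cancel in the average effect (.5 × .3 × .20 − .5 × .3 × .20 = 0), and for CSEC perpetration at 1%-5% false moderation is likely close to nominal.

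Finally, the SAP does not exclude interaction terms, and the measurement table listing the confounders is not in the documents. That is so, but re-estimation is triggered only by a whole-sample check that these imbalances pass. School as a covariate does not remove differences between students within a school.

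**Conclusion.** The point holds in conditional form. The SAP's only written balance check cannot see group-specific confounding, and Aim 2b relies on the same score to compare groups. For continuous outcomes and a moderately strong confounder (path .3), false moderation is about 12%-24% at within-group SMDs of ±.10. At a spurious difference of .12 it is 35%-75%. Each range runs from the rate with the screen to the rate without it, ignoring clustering. For a weak confounder (path .1, ±.10) it is close to 5%. In the 10% and 2.5% groups a one-sided imbalance is enough. Every rate depends on slopes that the documents do not give; the algebra of the whole-sample check does not. For rare binary outcomes the log-odds bias remains but is seldom declared. The Aim 2a average effect is outside this point. The change is worth making because Aim 2b is a stated aim and no new data are needed.

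**What to change.** For each Aim 2b moderator:

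1. Repeat the Step 3 table of standardized differences by condition within every moderator level, before any group effect is estimated.
2. Add moderator-by-confounder terms to the propensity model, or fit it within groups, where group size supports it. State whether the weights are also used in Aim 2b.
3. Put any confounder still imbalanced within a group into that group's outcome model.
4. Report effects descriptively for groups too small to balance, for example the expected n=181.

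The cost is analysis work: several propensity models instead of one. Weights will be more variable in small groups and possibly unstable at n=181, which is why the second step depends on group size and the fourth is needed.

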Aim 2a. Power analyses to support the sample size for the effectiveness analyses for our primary, secondary, and intermediary outcomes (see Figure 1) were conducted using G-Power 3.1. Power was set to .80 and $\alpha=.05$. Component A of the study will provide incidence rates which will be used to recalculate power prior to the implementation of Component B. For the purposes of this proposal, we calculated the MDES based on the proposed sample size. For the primary outcome of CSEC perpetration, there are no reliable incidence estimates in the literature on which to draw. With a sample size of 7,241 students enrolled, assuming conservative minimum incidence rates of CSEC perpetration of 1% to 5% (although we hypothesize it will be higher), we have power to detect an MDES difference between conditions, odds ratio (OR)=.49 to .75, respectively. Similarly, for secondary outcomes of CSEC victimization, we estimated a range of incidence rates from a conservation 5% to 50%+ based on literature discussed following for other types of victimization^{96, 132, 133} as well as rates of CSEC youth at increased risk (e.g., system involved, homeless)¹⁸⁻²⁰, which will be present in our sample based on DMPS data, we have the power to detect an MDES difference between conditions, odds ratio (OR)=.75 to .88, respectively. For secondary outcomes of TDV/SV perpetration and victimization, given past 12- months incidence rates¹³² (from nationally representative data from youth) of 63% for perpetration (of any type of TDV) and 69% for victimization (of any type of TDV), we have power to detect an MDES difference between conditions, odds ratio (OR)=.88 to .89. For sub-types of TDV (past 12-month incidence rates: physical victimization: 18%; sexual victimization: 18%; psychological victimization: 66%; physical perpetration: 12%; sexual perpetration: 12%; psychological perpetration: 62%)¹³², we have power to detect an MDES difference between conditions, odds ratio (OR)=.83 to .89, respectively. For the secondary outcome CSEC bystander action and opportunity and intermediary outcomes (i.e., knowledge, valuing of self and others, healthy relationship skills, bystander efficacy, perceptions of school social norms, prevention conversations with school personnel), the ANCOVA routine suggested power (.80) to detect a small difference between groups (MDES $d=.06$).

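### The 0.2 balance limit in the Aim 2a propensity analysis is looser than the effects the trial is sized to detect, and the outcome model names no baseline-outcome covariate to catch what it lets through

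*SAP*

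**What the plan says.** The SAP, Outcome Analyses (Aim 2a), describes a non-randomised comparison handled in four steps. Step 1 fits a logistic propensity model; for its contents, "we will consider all pertinent confounders and covariates (see Measurement Table 3"). Step 2 applies inverse probability weights. Step 3 checks each confounder in the score against one numerical rule, "balance = standardized mean differences $< |0.2|$ after adjustment", and "the propensity score model (Step 1) will be re-estimated until balance is reached". Step 4 then estimates the average treatment effect, with the propensity score and school as covariates. If weighting does not give optimal balance, other methods such as matching will be considered.

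For scale, Power Analyses (Aim 2a) gives the detectable effects. "With a sample size of 7,241 students enrolled", and "assuming conservative minimum incidence rates of CSEC perpetration of 1% to 5"%, "we have power to detect an MDES difference between conditions, odds ratio (OR)=.49 to .75, respectively". For bystander action and the intermediary outcomes, "the ANCOVA routine suggested power (.80) to detect a small difference between groups", given as d = .06.

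The pilot analysis (Proposed Analyses, Aim 1e) adjusts for the baseline measurement of the outcome. The Aim 2a text names no such covariate.

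**The concern.** Without randomisation, the weighting step is the main protection against selection bias, and the balance limit decides when that step is finished. A single limit on the standardized mean difference (SMD) is a weak test for a rare binary variable. When few students have the characteristic, a large ratio between arms is still a small fraction of a standard deviation. The rule is therefore most permissive, in relative terms, for uncommon baseline behaviours, which may be among the best predictors of the primary outcome.

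Confounding left in place at this stage would shift the effect estimate, and neither the p-value nor the confidence interval would show it. Depending on which arm starts lower, it could imitate a programme effect or hide one.

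**Working it through.** **Inputs from the SAP.** Limit 0.2; N = 7,241; perpetration 1% to 5%; detectable odds ratios (OR) .49 and .75; d = .06; "Power was set to .80 and $\alpha=.05".

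**Assumptions.** Arms are 1:1 (the SAP gives about .5 only for the pilot). Baseline CSEC perpetration is a checked confounder. The lower arm's baseline prevalence equals the SAP's 1% or 5%. Persistence k is the share of baseline perpetrators who perpetrate again, and it is varied.

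**1. The plan's own figures.** A two-proportion calculation with 7,241/2 per arm and 80% power gives detectable ORs of .494 at 1% and .751 at 5% with one-sided alpha .05, which reproduces .49 and .75. Two-sided alpha gives .440 and .722. For continuous outcomes the result is d = .058 one-sided and .066 two-sided. Sidedness is not stated in the SAP; that is a separate matter. The stated figures are used below.

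**2. What the limit accepts.** The SAP does not define the SMD denominator. With the usual averaged variance, solve (q − p) / √{[p(1 − p) + q(1 − q)] / 2} = limit for q:

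| Lower arm p | q at 0.2 | Ratio | q at 0.1 | Ratio |
|---|---|---|---|---|
| 1% | 4.15% | 4.15 | 2.27% | 2.27 |
| 5% | 10.29% | 2.06 | 7.41% | 1.48 |

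If only the lower arm's SD is used, the 0.2 limit accepts 1% versus 3.0% and 5% versus 9.4%. On the same SMD scale, the detectable ORs of .49 at 1% and .75 at 5% both correspond to about .059. The limit is thus about 3.4 times the detectable effect (0.2 / 0.059).

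**3. Bias in the primary outcome with no programme effect.** Let r0 be the follow-up risk among students who were not baseline perpetrators, set so that the lower arm's follow-up rate equals its baseline: r0 = p(1 − k)/(1 − p). The other arm's risk is f = qk + (1 − q)r0, and the spurious OR is [p/(1 − p)] / [f/(1 − f)].

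- p = 1%, k = 30%: r0 = .01 × .7/.99 = .00707; f = .0415 × .3 + .9585 × .00707 = .0192; OR = .0101/.0196 = .52.
- p = 5%, k = 30%: r0 = .05 × .7/.95 = .0368; f = .1029 × .3 + .8971 × .0368 = .0639; OR = .0526/.0683 = .77.

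| Persistence k | OR at 1% | OR at 5% |
|---|---|---|
| 10% | .77 | .94 |
| 20% | .62 | .85 |
| 30% | .52 | .77 |
| 33% | .49 | .75 |
| 40% | .44 | .71 |
| Stated detectable OR | .49 | .75 |

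The bias matches the detectable effect at about 33% persistence and exceeds it only above that. With 10% prevalence in the lower arm the limit passes 16.8% in the other (1.68-fold), and the spurious OR at 30% persistence is .85.

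**4. Continuous outcomes.** For one confounder, bias in d ≈ SMD × r, where r is its correlation with the outcome: .2 × .3 = .06, equal to the stated detectable effect; .2 × .5 = .10.

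**5. Would 0.1 alone be enough?** At k = 30%:
- 1% case: f = .0227 × .3 + .9773 × .00707 = .0137, so OR = .0101/.0139 = .73.
- 5% case: f = .0741 × .3 + .9259 × .0368 = .0563, so OR = .0526/.0597 = .88.

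The bias is roughly halved on the log scale but not removed.

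**The case against.** **The limit is a ceiling.** A covariate entered in a logistic propensity model is normally balanced almost completely by the weights. In a simulation with N = 7,241, 1:1 arms, baseline perpetration and one continuous confounder both in the model, and raw gaps as large as those above, the mean weighted SMD was .006 (1% case) and .003 (5% case). Leaving out an arm-specific association between the two confounders raised it to only about .035. This stands: a reader might infer that the trial will end with a twofold or fourfold imbalance, and nothing in the documents supports that as the expected result. It also means a tighter limit should be easy to meet.

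**The bias need not exceed the detectable effect.** Also correct. At 30% persistence, .52 and .77 fall just short of .49 and .75. The documents give no persistence figure, so a reader cannot conclude that confounding will outweigh the effect.

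**The inputs are pessimistic or unseen.** The SAP calls 1% to 5% conservative minimums and expects higher. They are outcome incidences, used here as baseline prevalences. The detectable effects are what the proposed sample size can detect, to be recalculated after Component A; they are not target effects. Table 3 is not in the documents, so whether baseline perpetration is checked is unknown. The SAP does intend to include all measured confounders that predict selection and outcome, and says all enrolled cases have baseline data, so its inclusion is plausible. If it were left out, no limit would apply to it.

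**Other safeguards exist.** The fallback to other methods and the use of the score as a covariate may help. However, 0.2 is the only number given for when balance is adequate. A gap that survives weighting also shows that the score has not captured that variable, so re-entering the same score is not a dependable repair.

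**Conclusion.** The point holds as a weakness in a pre-specified acceptance rule, not as a prediction of bias. Step 3 would certify as balanced an imbalance about 3.4 times the detectable effect on the same scale. If such a gap occurred on baseline perpetration, a programme with no effect could show an OR of .44 to .62 in the 1% case or .71 to .85 in the 5% case, over 20% to 40% persistence. These figures rest on assumed persistence, on baseline perpetration being a checked confounder, and on prevalence at the SAP's minimum rates; higher prevalence makes the bias smaller. For continuous outcomes the bias reaches d = .06 at r = .3.

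The documents do not support the stronger reading that the primary analysis is invalid as planned. This is a cheap improvement, best made before outcome data are seen.

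**What to change.** 1. In Step 3, replace |0.2| with |0.1| for all confounders and state the SMD denominator.
2. Include the baseline value of each outcome (baseline CSEC perpetration for the primary outcome) in the Step 1 propensity model and as a covariate in the Step 4 outcome model, as Aim 1e already does for the pilot. This matters more than the cut-off, because 0.1 alone still admits 1% versus 2.3%.
3. Name the fallback if weighting misses 0.1: weights that balance the covariates directly while targeting the average treatment effect, such as entropy balancing or covariate-balancing propensity scores.

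A further rule requiring the weighted prevalence ratio to lie within .9 to 1.1 is not advised. At 1% prevalence there would be only about 36 baseline perpetrators per arm (7,241/2 × .01). By chance, only about 33% of perfectly randomised trials of this size would meet the rule, and about 67% at 5% prevalence.

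The cost is a short SAP edit, slightly more variable weights and a small loss of effective sample size. No new data are needed if baseline perpetration is already measured, which the missing Table 3 would confirm.

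### The SAP names a population-level ATE, but Step 4 does not say that the IPTW weights are used, and for binary outcomes it reports a covariate-conditional odds ratio, which is a different quantity

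*SAP*

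**What the plan says.** All of this is in the SAP, Proposed Analyses, Aim 2a and 2b.

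- **Target.** "The experimental effect of interest will be the Average Treatment Effect (ATE), which is the population-level average effect of condition". The sentence goes on to cover both primary and secondary outcomes.
- **Step 2.** "We will use inverse probability weighting (IPTW) to adjust for confounding". Other methods, with matching as the example, may be considered if balance is not optimal.
- **Step 3.** Balance means standardised mean differences below 0.2 in absolute value after adjustment, computed on the weighted sample.
- **Step 4, continuous outcomes.** The effects are "differences between experimental conditions at post-test and follow-up on outcomes (for continuous measures), the propensity score as a covariate".
- **Step 4, categorical outcomes.** "For categorical variables, logistic regression will be used to examine differences in prevalence by condition". Condition is the independent variable. Because there are too few schools for multilevel modelling, "thus, school will be included as a covariate". Results are judged on p-values, confidence intervals and standardised differences, "as well as the directionality of included path coefficients, and odds ratios".

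Nothing says whether Step 4 is fitted with the weights. No standardisation, risk difference or marginal odds ratio is specified for binary outcomes.

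**The concern.** IPTW followed by a weighted comparison of the two conditions estimates a population-average effect. A logistic coefficient from a model that also contains covariates estimates an effect within levels of those covariates. Odds ratios are non-collapsible, so the two differ whenever the covariates predict the outcome and the effect is not null, even with no residual confounding.

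Two things are at stake. First, analysts following the same text could fit a weighted model, a propensity-adjusted model or both, obtain different odds ratios, and label each one the ATE. Second, if the weights are not used in Step 4, the balance shown in Step 3 belongs to a different analysis. This is a quasi-experimental comparison, so the causal claim rests on that link.

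**Working it through.** **1. The steps side by side**

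| Step | What is stated | What it targets |
|---|---|---|
| Estimand | Population-level ATE | Marginal effect |
| 2 and 3 | IPTW; balance on the weighted sample | Marginal effect |
| 4, continuous | Difference with the propensity score as covariate | Adjusted mean difference; non-collapsibility does not arise |
| 4, categorical | Logistic regression on condition, school as covariate, odds ratio | Conditional odds ratio (on school for certain, on the propensity score by the likely reading) |

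**2. The plan's own detectable odds ratios**

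Inputs from the SAP, Power Analyses, Aim 2a: N = 7,241, power .80, alpha .05. Equal arms are assumed, because an assignment rate of about .5 is stated only for the open pilot. That gives 7,241/2 = 3,620.5 per arm. With p1 = p0·OR/(1 − p0 + p0·OR), I solved a pooled-variance two-proportion test for 80% power.

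| Rate | Stated | One-sided .05 | Two-sided .05 |
|---|---|---|---|
| 1% | .49 | .494 | .440 |
| 5% | .75 | .751 | .722 |
| 63% (any TDV perpetration) | .88 to .89 | .887 | .873 |
| 69% (any TDV victimization) | .88 to .89 | .883 | .869 |

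The stated values reproduce as one-sided; the SAP does not give the sidedness. They come out with no covariate in the calculation.

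**3. From a conditional to a marginal odds ratio**

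Model: logit P(Y=1) = a + ln(OR_c)·T + s·Z, with Z standard normal. Here s is the spread of outcome risk, on the logit scale, carried by the covariates in the model. The documents do not give s, so it is varied.

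- Choose a so that the average of expit(a + sZ) equals p0.
- Then p1 is the average of expit(a + ln OR_c + sZ).
- The marginal OR is [p1/(1 − p1)] / [p0/(1 − p0)].

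Example: p0 = .63, OR_c = .88, s = 1. The risk difference is −.0251, so p1 = .6049. The odds are .6049/.3951 = 1.531 and .63/.37 = 1.703, and their ratio is .899. On the log scale, ln(.88)/ln(.899) = .1278/.1065 = 1.20.

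Marginal OR when the model's OR is the conditional value shown:

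| Rate | Conditional OR | s = 0.25 | s = 0.5 | s = 1.0 | s = 1.5 |
|---|---|---|---|---|---|
| 1% | .49 | .490 | .491 | .494 | .504 |
| 5% | .75 | .751 | .752 | .762 | .778 |
| 50% | .88 | .882 | .886 | .900 | .914 |
| 63% | .88 | .882 | .886 | .899 | .913 |
| 69% | .89 | .891 | .895 | .907 | .919 |

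At 63% the gap is .002, .006, .019 and .033. The log odds ratio is overstated by 1.5%, 5.6%, 20% and 40%, and the risk difference is −3.0, −2.9, −2.5 and −2.2 percentage points. At OR_c = 1 the term ln(OR_c) is 0, so p1 = p0 for every s and the gap is zero.

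**4. Check with a propensity score in the model**

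Simulation with one confounder and 2,000,000 records per scenario; propensity-covariate OR against IPTW marginal OR:

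| Rate | Weak | Moderate | Strong |
|---|---|---|---|
| 63% | .882 vs .889 | .878 vs .895 | .877 vs .909 |
| 5% | .747 vs .750 | .753 vs .766 | .758 vs .786 |

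At 1% the gap is at most about .01. One confounder is close to the worst case, because the propensity score then carries all of the prognostic information. With three confounders at 66%, the log odds ratio was overstated by about 26% when all were strong and acted in the same direction. It was overstated by only about 2% when one confounder predicted condition in the opposite direction.

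**The case against.** The strongest reply is textual. The covariate clause, "on outcomes (for continuous measures), the propensity score as a covariate", is attached to continuous measures, and an adjusted linear difference is not subject to non-collapsibility. The categorical sentence does not name the propensity score. The phrase "including the propensity score and school as covariates in all models" comes from the mediation and moderation section (Aim 2b) and does not govern Aim 2a. Weighting, checking balance on the weighted sample and then estimating effects reads naturally as one weighted analysis. Combining weights with covariate adjustment is also a recognised choice, with some merit when residual imbalance up to 0.2 is tolerated.

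Much of this stands. A reader might infer that the SAP enters the propensity score in every logistic model, but that is only the likely reading: Step 4 is labelled propensity score-adjusted, and the sentence before the categorical one speaks of adjusting for the score. A reader might also infer a fixed percentage of overstatement for common outcomes. The documents give no confounder strengths, and the excess nearly vanishes when confounders act in different directions. Nor is the significance test invalidated on this ground, since the gap is zero under the null.

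The reply does not remove the central gap. School is a covariate on any reading, so the odds ratio is conditional whatever happens to the propensity score. No step turns it into an ATE, and the use of the weights in Step 4 is left unsaid.

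**Conclusion.** The point holds for binary outcomes. The stated estimand is marginal and the reported odds ratio is conditional. The SAP neither connects the two nor says that the model is weighted.

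The size is an assumption-dependent range. It is about .002 to .03 on the odds-ratio scale for outcomes near 50% to 66%, in the direction away from 1. The upper part needs covariates that predict the outcome strongly (s of 1 to 1.5). If the weights are carried forward and only school is conditioned on, the gap depends on how much risk varies between schools, which the documents do not give; at s = 0.25 it is about .002.

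For the primary outcome at 1% to 5%, the shift is .012 or less for s up to 1 and reaches about .03 only at 5% with s = 1.5. The consequence is therefore mainly for the common secondary outcomes: TDV, and CSEC victimization if it is near 50%. The stated detectable values of .88 to .89 give a sense of scale there, but they are planning figures and not a threshold that an estimate must cross.

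Separately, if the weights are dropped, the Step 3 balance result does not describe the Step 4 model, whatever the size of the odds-ratio gap.

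**What to change.** - State that Step 4 is fitted with the final IPTW weights for which balance was shown.
- For binary outcomes, predict each enrolled student's risk under both conditions from the fitted model, average over all enrolled students, and report the marginal risk difference and marginal odds ratio. Label any covariate-adjusted odds ratio as conditional.
- For continuous outcomes, the propensity score may stay as a covariate alongside the weights; the SAP should say whether it does.
- If matching replaces IPTW, use a form that keeps the ATE, or relabel the estimand.

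The cost is a change of SAP wording and one standardisation step, with no new data. Odds ratios for common outcomes may look slightly less favourable.
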